Appendix B Exclusionary Drugs

The following medications are metabolized by CYP450 enzymatic pathways and have a narrow therapeutic window. The use of these medications from one day prior to Randomization (Day -1) through Study Week 24 is prohibited.

- digoxin
- theophylline
- terfenadine
- tizanidine
- quinidine
- phenytoin and its derivatives
- taxane chemotherapeutic agents
- cyclosporine
- mTOR inhibitors (sirolimus, tacrolimus)
- ergot alkaloids
- antipsychotic medications (specifically pimozide, thioridazine)
- fentanyl and derivatives (e.g., alfentanil and sufentanil)

Appendix C ESA and Parenteral Iron Dose-Adjustments

Weeks 1 - 4

- ESA doses are not to be adjusted or held during Weeks 1 through 4 unless one or more confirmed hemoglobin values (i.e., at least 2 consecutive measurements) or the patient's clinical status necessitates such due to a clear and present safety risk
- Parenteral iron doses are not to be adjusted or held during Weeks 1 through 4
- Patients not receiving parenteral iron products during Screening must not be started on these during Weeks 1 through 4
- The Medical Monitor must be contacted prior to any contemplated ESA or parenteral iron dose changes

Weeks 5 – 24

- Changes to ESA dosing must be based on hemoglobin values that have been confirmed (i.e., at least 2 consecutive measurements)
- Do not increase the dose more frequently than once every 4 weeks. The recommended dose increase at any given time is 25%
- Decreases in dose may occur more frequently than once every 4 weeks. The recommended minimum duration between dose reductions is 3 weeks
- If the hemoglobin rises rapidly (e.g., more than 1 g/dL in any 2-week period), reduce the dose by 25%. A greater reduction may be made, if rise in hemoglobin is unacceptably rapid
- The Medical Monitor must be contacted prior to any contemplated ESA dose changes that depart from the above protocol requirements and recommendations unless clinical urgency precludes this. If the Medical Monitor is not contacted in advance, please send a notification within 24 hours that an off-protocol ESA dose change was made
- Patients not receiving parenteral iron products must not be started on these during Weeks 5 through 24
- Parenteral iron doses are not to be adjusted or held during Weeks 5 through 24, unless approved by the Medical Monitor

Appendix D Laboratory Measurements

Laboratory	Panel Name	Tests Included
Central	Panel 1: Chemistry [CHEM]	Sodium, potassium, chloride, bicarbonate (or CO ₂), calcium, phosphate, alanine aminotransferase (ALT), aspartate aminotransferase (AST), blood urea nitrogen (BUN) creatinine, total bilirubin, direct bilirubin, alkaline phosphatase, albumin, glucose
Central	Panel 2: Lipids [LIP]	Total cholesterol, low density lipoprotein (LDL) cholesterol, high density lipoprotein (HDL), triglycerides
Central	Panel 3: Inflammation 1 [INFL1]	serum amyloid A, hepcidin
Central	Panel 4: Special RBC Indices [SPRBC]	reticulocyte hemoglobin concentration (CHr), % hypochromic red cells (%HRC)
Central	Panel 5: Hematology [HEME]	Hemoglobin, hematocrit, reticulocyte count, red blood count (RBC) indices (e.g., mean corpuscular volume (MCV), red cell distribution width (RDW), platelets, white blood count (WBC), WBC differential
Central	Panel 6: Iron Indices [IRON]	TSAT, ferritin, iron, total iron binding capacity (TIBC)
Central	Panel 7: PK [PK]	COR-001
Central	Panel 8: Cardiac Markers [CARD]	Troponin T, NT-proBNP
Central	Panel 9: Infection Screen [INFEC]	HIV 1 and 2, Hepatitis B surface antigen, Hepatitis B surface antibody, Hepatitis C antibody, mycobacterium tuberculosis blood test (i.e., interferon gamma release assay)
Central	Panel 10: Anti-Drug Antibodies [ADA]	Anti-COR-001 binding antibodies and neutralizing antibodies (if binding antibodies are detected)
Central	Panel 11: Inflammation 2 [INFL2]	Total and free IL-6
Central	Panel 12: Future biomarkers [BIO]	Future cardiac, renal, and hematologic markers, including gene variations, ribonucleic acid, or protein markers
Central	Panel 13: B-Vitamins [BVIT]	B-12, folate
Central	Other individual tests	Screening (total) IL-6, genotype, intact parathyroid hormone [PTH], lipoprotein a [Lp(a)], pregnancy [β -hCG in women of childbearing potential only], follicle-stimulating hormone (FSH), stool occult blood, pre-albumin, hsCRP
Local	Coagulation	International normalized ratio (INR) (warfarin-treated patients only)

Appendix E FACIT-F

FACIT-F (Version 4)

Below is a list of statements that other people with your illness have said are important. Please circle or mark one number per line to indicate your response as it applies to the past 7 days.

		Not at all	A little bit	Some- what	Quite a bit	Very much
PHYSICAL WELL-BEING						
GP1	I have a lack of energy	0	1	2	3	4
GP2	I have nausea	0	1	2	3	4
GP3	Because of my physical condition, I have trouble meeting the needs of my family	0	1	2	3	4
GP4	I have pain	0	1	2	3	4
GP5	I am bothered by side effects of treatment	0	1	2	3	4
GP6	I feel ill	0	1	2	3	4
GP7	I am forced to spend time in bed	0	1	2	3	4

		Not at all	A little bit	Some- what	Quite a bit	Very much
SOCIAL/FAMILY WELL-BEING						
GS1	I feel close to my friends	0	1	2	3	4
GS2	I get emotional support from my family	0	1	2	3	4
GS3	I get support from my friends	0	1	2	3	4
GS4	My family has accepted my illness	0	1	2	3	4
GS5	I am satisfied with family communication about my illness	0	1	2	3	4
GS6	I feel close to my partner (or the person who is my main support)	0	1	2	3	4
Q1	Regardless of your current level of sexual activity, please answer the following question. If you prefer not to answer it, please mark this box  and go to the next section.					
GS7	I am satisfied with my sex life	0	1	2	3	4

FACIT-F (Version 4)

Please circle or mark one number per line to indicate your response as it applies to the past 7 days.

EMOTIONAL WELL-BEING		Not at all	A little bit	Some-what	Quite a bit	Very much
GE1	I feel sad.....	0	1	2	3	4
GE2	I am satisfied with how I am coping with my illness.....	0	1	2	3	4
GE3	I am losing hope in the fight against my illness.....	0	1	2	3	4
GE4	I feel nervous.....	0	1	2	3	4
GE5	I worry about dying.....	0	1	2	3	4
GE6	I worry that my condition will get worse.....	0	1	2	3	4

FUNCTIONAL WELL-BEING		Not at all	A little bit	Some-what	Quite a bit	Very much
GF1	I am able to work (include work at home).....	0	1	2	3	4
GF2	My work (include work at home) is fulfilling.....	0	1	2	3	4
GF3	I am able to enjoy life.....	0	1	2	3	4
GF4	I have accepted my illness.....	0	1	2	3	4
GF5	I am sleeping well.....	0	1	2	3	4
GF6	I am enjoying the things I usually do for fun.....	0	1	2	3	4
GF7	I am content with the quality of my life right now.....	0	1	2	3	4

FACIT-F (Version 4)

Please circle or mark one number per line to indicate your response as it applies to the past 7 days.

ADDITIONAL CONCERNS		Not at all	A little bit	Some- what	Quite a bit	Very much
HI7	I feel fatigued	0	1	2	3	4
HI12	I feel weak all over	0	1	2	3	4
An1	I feel listless (“washed out”)	0	1	2	3	4
An2	I feel tired	0	1	2	3	4
An3	I have trouble starting things because I am tired.....	0	1	2	3	4
An4	I have trouble finishing things because I am tired	0	1	2	3	4
An5	I have energy	0	1	2	3	4
An7	I am able to do my usual activities.....	0	1	2	3	4
An8	I need to sleep during the day	0	1	2	3	4
An12	I am too tired to eat	0	1	2	3	4
An14	I need help doing my usual activities.....	0	1	2	3	4
An15	I am frustrated by being too tired to do the things I want to do.....	0	1	2	3	4
An16	I have to limit my social activity because I am tired.....	0	1	2	3	4

Appendix F Guidance on Contraception

For the purposes of the proposed study, **“highly effective” contraceptive methods** are defined as those, alone or in combination, that result in a low failure rate (i.e., less than 1 percent per year) when used consistently and correctly, and include the following:

- Surgical sterilization at least 6 months before Study Drug administration
- Implants
- LNG and Copper T IUDs
- Sexual abstinence

Patients who prefer methods which evidence a higher (6-9%) failure rate with typical use will be required to employ at least two methods of contraception concurrently. These methods include the following:

- Injectable hormone depots
- Oral contraceptive pill
- Hormone patch
- Vaginal ring

Periodic abstinence (e.g., calendar, ovulation, symptothermal, post-ovulation methods) and withdrawal are NOT acceptable methods of contraception.

http://www.cdc.gov/reproductivehealth/unintendedpregnancy/pdf/contraceptive_methods_508.pdf for a list of contraceptive methods and effectiveness.

Investigators may contact the Medical Monitor to discuss questions regarding appropriate contraception.. The guidance will follow that described in the document <http://www.covance.com/content/dam/covance/assetLibrary/posters/KamACCP15.pdf> and will comply with FDA M3(R2).

1. INTRODUCTION

This Statistical Analysis Plan (SAP) describes the statistical methods that will be used during the analysis and reporting of data collected under Corvidia Therapeutics Protocol COR-001-01. This SAP should be read in conjunction with the study protocol and electronic case report forms (eCRFs). This version of the SAP has been developed using Protocol amendment 2 dated 20-Sep-2016 and the final eCRFs dated 05-JUL-2016.

Pharmacokinetic and pharmacokinetic-pharmacodynamic modeling analyses are described in the Data Analysis Plan for Pharmacokinetic and Pharmacokinetic-Pharmacodynamic Modeling.

1.1 STUDY OBJECTIVES

1.1.1 Primary Objective

The primary objective of the study is to evaluate the safety of multiple doses of COR-001.

1.1.2 Secondary Objectives

The secondary objectives of the study include the following:

- To model the relationship of COR-001 pharmacokinetics and primary pharmacodynamics as assessed by free and total serum Interleukin-6 (IL-6), high-sensitivity C-reactive protein (hsCRP) and serum amyloid A (SAA)
- To evaluate the secondary pharmacodynamic effects of COR-001 as assessed by:
 - Hemoglobin
 - Erythropoiesis stimulating agent (ESA) resistance index (ERI)
 - Systemic iron availability (transferrin saturation (TSAT), reticulocyte hemoglobin concentration (CHr) and absolute reticulocyte count)
 - Systemic iron stores (serum ferritin and supplemental iron dose requirements)
 - Malnutrition-inflammation (pre-albumin, albumin)
 - Serum cardiac biomarkers (Troponin T and N-terminal pro-B-natriuretic peptide [NT-proBNP])
 - Left ventricular mass index (LVMI) by non-contrast Myocardial Resonance Imaging (MRI)
 - Physical function by handgrip strength and symptoms of fatigue
- To investigate the immunogenicity of COR-001

1.2 STUDY ENDPOINTS

1.2.1 Primary Safety Endpoint

Primary safety endpoint is characterization of the Maximally Tolerated Dose (MTD) or to establish that the highest dose examined did not exceed the MTD. MTD will be characterized based on the Dose-Limiting Toxicities (DLTs) defined in [Section 1.2.2](#). Potential DLTs will be identified programmatically and through clinical review of adverse event information and lab information.

1.2.2 Secondary Safety Endpoints

- Description of the frequency of DLTs by treatment group.
- Dose-Limiting Toxicities are identified as follows:
 1. Confirmed (i.e., at least 2 consecutive measurements) Grade 3 neutropenia and representing a decline of > 25% from baseline
 2. Serious adverse events of infection in the presence of confirmed (i.e., at least 2 consecutive measurements) Grade 2 or higher new onset lymphopenia or new onset neutropenia.
 3. \geq Grade 3 alanine aminotransferase (ALT) or aspartate aminotransferase (AST)
 4. \geq Grade 4 hematologic toxicity
 5. \geq Grade 3 non-hematologic toxicity

DLT was defined as any toxicity the relationship of which to the investigational agent cannot be ruled out as follows:

- With the exception of Grade 3 non-hematologic events, Grade 3 (or higher) CTCAE toxicity of above events having an assessed relationship to the Study Drug of “definitely”, “probably”, “possibly”, or “unlikely” will be considered DLTs.
- Grade 3 non-hematologic toxicities having an assessed relationship to the Study Drug of “probably”, or “possibly” will be considered DLTs.

Note: “non-hematologic events” refer to DLT criteria 1, 2, 3, and 5 above.

- Description of the frequency of the events of interest by treatment group. The events of interest included:
 - Severe infusion-related reactions
 - Hypersensitivity reaction during the Study Drug infusion
 - Anaphylaxis occurring at any time, even if considered unrelated to the Study Drug

Infusion-related reactions, hypersensitivity reactions, and anaphylaxis will be identifiable from a check box on the AE CRF and the CTCAE grade of the event and supported by data collected on the Infusion-related reaction/Hypersensitivity/Anaphylaxis CRF. The protocol defines hypersensitivity reactions and infusion-related reactions by their temporal relationship based on timing of onset during the study drug infusion.

- Description of additional safety assessments by treatment group: adverse events, vital signs, ECG, clinical laboratory, and anti-drug antibodies (binding and neutralizing).

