	
limiting toxicities occurring through Study Day 21 in the 8 actively treated patients in the current cohort (see Figure 2). In addition, pharmacokinetic and pharmacodynamic results will be reviewed to assess the appropriateness of the next planned dose and to guide revision of the next dose to be evaluated, if necessary.
 
Patients will undergo an up to 4-week Screening Period during which the ESA dose and parenteral iron doses must have been stable, as defined in the inclusion and exclusion criteria. All patients randomized will be continued on ESA and parenteral iron (if being given).
 
Patients meeting the entry criteria will generally be randomized on Day 1. The first dose of Study Drug will be administered during dialysis. Administration of the first dose of Study Drug will define Study Day 1. Additional visits will follow the schedule of events (see Appendix A: Schedule of Events). All subsequent Study Drug infusions will also be administered during dialysis and study visits will coincide with regularly scheduled dialysis treatments. Patients dropping out (i.e., prematurely discontinuing Study Drug treatment) for reasons unrelated to safety may be replaced in order to maintain the randomization ratio within each cohort.
 
Following the 12-week Treatment Period, patients will be followed for an additional 12 weeks for safety in the Safety Follow-Up Period. Patients will have completed their primary study participation at Week 24 (end of the Safety Follow-Up Period). Limited blood sampling will occur on Week 35 for anti-drug antibodies, pharmacokinetics, and IL-6 measurements as part of an Extended Follow-Up Period.

Study Periods:
	
The total study duration for an individual patient will be approximately 9 months, excluding the Screening Period.
 
Initial Screening Period: up to 2 weeks [Days -28 to -15]
 
 •Starts with the first date that Initial Screening procedures were performed. The first procedure also defines the initial screening visit date. 
Full Screening Period: up to 2 weeks [Days -14 through Day -1]
 
 •Starts with the date of the Week -2 Visit 
Treatment Period: 12 weeks [Week 1, Day 1 through Week 12]
 
Safety Follow-Up Period: 12 weeks [Weeks 13 through 24]
 
Extended Follow-Up Period: 10 weeks [Weeks 25 through 35]

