3 INVESTIGATIONAL PLAN

3.1 Overall Study Design and Plan: Description

This is a randomized, double-blind, placebo-controlled trial designed to evaluate the safety, pharmacokinetics, and pharmacodynamic effects of multiple doses of COR-001 or placebo administered to sequential cohorts of hemodialysis patients.

Ten hemodialysis patients will be randomized to COR-001 or placebo within each dosing cohort. When a higher dose than studied in a prior cohort is being initiated, the first 2 (sentinel) patients in that cohort will be randomized 1:1 to COR-001 or placebo; the remaining patients will be randomized at least 48 hours later in a 7:1 ratio of COR-001 to placebo.

Prior to dose escalation (i.e., higher total dose than studied in the preceding cohorts), there will be a formal safety review by the Safety Review Committee (SRC), which will include at least one nephrologist. The SRC will specifically determine whether the maximum tolerated dose (MTD) has been exceeded based on protocol-defined dose-limiting toxicities occurring through Study Day 21 in the 8 actively-treated patients in the current cohort (see [Figure 2](#)). In addition, PK and PD results will be reviewed to assess the appropriateness of the next planned dose and to guide revision of the next dose to be evaluated, if necessary. The planned doses are shown in [Table 2](#). These doses may be adjusted based on accruing data; however, the maximum dose to be studied will not exceed the planned total dose in Cohort 4 (60 mg every 14 days [6 doses]).

A single interim analysis (described in [Section 11.5](#)) is planned to enable future program planning.

Patients will undergo a Screening Period during which the ESA dose and parenteral iron doses must have been stable, as defined in the inclusion and exclusion criteria. Patients randomized to both COR-001 and placebo will be continued on ESA and parenteral iron (if being given).

Patients meeting the entry criteria will be randomized on Day 1 (a dialysis day), following which they will receive the first dose of Study Drug during dialysis. Additional visits will follow the schedule of events ([Appendix A](#)). All subsequent Study Drug infusions will also be administered during dialysis and study visits will coincide with regularly scheduled dialysis treatments. Patients dropping out (i.e., prematurely discontinuing Study Drug treatment) for reasons unrelated to safety may be replaced.

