3.2 Study Schematic

Figure 2 Dose Escalation Schematic

- ¹ If the MTD is not exceeded, dose escalation may continue.
- ² If the MTD is exceeded, a lower dose, including previously studied dose, may be selected.

The MTD assessment will be based on safety data from Weeks 1 to 3. If more than 2 of 8 active patients in a cohort experience a DLT, the MTD will be considered to have been exceeded.

The planned doses shown here may be adjusted based on accruing PK, PD, and safety data. The highest dose that will be studied is a cumulative dose of 360 mg. Expansion cohorts to further evaluate doses below the dose that exceeded the MTD may be initiated at any time.

The randomization ratio within each cohort will be 8:2 (COR-001 to placebo).

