4.4 Dose-Limiting Toxicities, Maximum Tolerated Dose, and Stopping Rules

Prior to dose escalation (i.e., higher total dose than studied in the preceding cohorts), there will be a formal safety review by the Safety Review Committee. The safety review required for dose escalation will include 21 days of treatment data from the preceding cohort(s).

Dose-Limiting Toxicities are defined as follows:

1. Confirmed Grade 3 neutropenia and representing a decline of > 25% from baseline
2. Serious adverse events of infection in the presence of confirmed Grade 2 or higher new onset lymphopenia or new onset neutropenia.
3. \geq Grade 3 ALT or AST
4. \geq Grade 4 hematologic toxicity
5. \geq Grade 3 non-hematologic toxicity

DLT will be defined as any toxicity the relationship of which to the investigational agent cannot be ruled out as follows:

- With the exception of Grade 3 non-hematologic events, Grade 3 (or higher) CTCAE toxicity of above events having an assessed relationship to the Study Drug of “definitely”, “probably”, “possibly”, or “unlikely” will be considered DLTs.

Note: “non-hematologic events” refer to DLT criteria 1, 2, 3, and 5 above.

- Grade 3 non-hematologic toxicities having an assessed relationship to the Study Drug of “definitely”, “probably” or “possibly” will be considered DLTs.

In addition, dose-escalation may be halted for any safety trend believed to be dose-related that would pose an unacceptable risk if dose were escalated.

If more than 2 of 8 COR-001-treated patients in a cohort experience a DLT, the MTD will be exceeded and stopping criteria for that dose will have been met.

In addition, if 1 of 8 COR-001-treated patients in a cohort experiences a Grade 4 or 5 DLT, the dose will not be escalated.

Stopping Rules for Individual Patients

Severe (i.e., \geq Grade 3): infusion-related reactions, cardiopulmonary infusion reactions, anaphylaxis, or hypersensitivity (see [Section 8.2](#))

Stopping Rules for the Entire Study

If ≥ 5 COR-001-treated patients develop anaphylaxis at any point during the entire study, enrollment and further dosing will be stopped.

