1.3 SUMMARY OF THE STUDY DESIGN

1.3.1 General Study Design and Plan

[figure not shown]
This is a randomized, double-blind, placebo-controlled trial designed to evaluate the safety, pharmacokinetics, and pharmacodynamic effects of multiple doses of COR-001 or placebo administered to sequential cohorts of hemodialysis patients.

Within each dosing cohort ten hemodialysis patients will be randomized to COR-001 or placebo at ratio of 8 to 2. Prior to dose escalation there will be a formal safety review by the Safety Review Committee (SRC). The SRC will specifically determine whether MTD has been exceeded based on protocol-defined DLT occurring through Study Day 21 in the 8 actively-treated patients in the current cohort (see Figure 1). In addition, pharmacokinetic and pharmacodynamic results will be reviewed to assess the appropriateness of the next planned dose and to guide revision of the next dose to be evaluated, if necessary. The planned doses are shown in Table 1. These doses may be adjusted based on accruing data; however, the maximum dose to be studied will not exceed the planned total dose in Cohort 4 (60 mg every 14 days [6 doses]).

A single interim analysis was planned to enable future program planning.

Patients will undergo an up to 4-week Screening Period. Those who meet the entry criteria will be randomized on Day 1 (a dialysis day) (or Day -1 with approval) and will receive the first dose of study drug during dialysis. Additional visits will follow the schedule of events (Appendix A, Section 15.1 of protocol). All subsequent study drug infusions will also be administered during dialysis and study visits will coincide with regularly scheduled dialysis treatments. Patients dropping out for reasons unrelated to safety may be replaced. Following the 12-week Treatment Period, patients will be followed for an additional 12 weeks for safety. The patients will have completed their primary study participation at Week 24 (end of the Safety Follow-Up Period). Sparse blood samples will be additionally collected on Week 35 for anti-drug antibodies, pharmacokinetics, and IL-6 measurements as part of an Extended Follow-Up Period.

Figure 1 Dose Escalation Schematic

The MTD assessment will be based on safety data from Weeks 1 to 3. If more than 2 of 8 active patients in a cohort experience a DLT, the MTD will be considered to have been exceeded.

¹If the MTD is not exceeded, dose escalation may continue.

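### On the nominal schedule no blood count falls between dose 2 (Day 15) and the Day 21 DLT cutoff, so the MTD tally for cytopenias normally rests on dose-1 counts

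*SAP*

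**What the plan says.** Characterizing the MTD is the primary safety endpoint (Protocol 3.1.2, SAP 1.2.1). Three of the five DLT criteria depend on blood counts:

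- Criterion 1 in SAP 1.2.2 is "Confirmed (i.e., at least 2 consecutive measurements) Grade 3 neutropenia and representing a decline of > 25% from baseline".
- Criterion 2 combines a serious infection with a lymphopenia or neutropenia confirmed in the same way.
- Criterion 4 is hematologic toxicity of Grade 4 or worse, with no confirmation required.

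A note in Protocol 4.4, repeated in SAP 1.2.2, says that non-hematologic events "refer to DLT criteria 1, 2, 3, and 5 above". Criteria 1 and 2 therefore carry the non-hematologic label although they turn on cell counts.

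The time limit appears in several places. In Protocol 3.1 the Safety Review Committee (SRC) judges whether the MTD was exceeded from "dose-limiting toxicities occurring through Study Day 21 in the 8 actively-treated patients in the current cohort". SAP 1.3.1 bases it on "protocol-defined DLT occurring through Study Day 21 in the 8 actively-treated patients in the current cohort". Protocol 3.2 states: "The MTD assessment will be based on safety data from Weeks 1 to 3". The DLT summary in SAP 8.3 covers Study Days 1 to 21.

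Two rules use DLTs. The MTD is exceeded when more than 2 of 8 active patients have one. Separately, Protocol 4.4 says "if 1 of 8 COR-001-treated patients in a cohort experiences a Grade 4 or 5 DLT, the dose will not be escalated", and gives no day. The same section adds that "dose-escalation may be halted for any safety trend believed to be dose-related".

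**The concern.** The primary objective is the safety of multiple doses, and a 21-day window contains dose 2. If no scheduled count can reflect dose 2, the window works as a single-dose assessment for cytopenias. A conclusion that a dose did not exceed the MTD would then rest, as far as scheduled counts go, on the first infusion.

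Neutrophils are a relevant signal for this drug. Protocol 3.7 names white-cell and neutrophil changes as the one exception to the absence of laboratory trends in the rheumatoid arthritis study.

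There is also a gap in the confirmation rule. A count first low on Day 15 can be confirmed on schedule only on Day 22. Neither document says whether such an event still qualifies under criteria 1 and 2.

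**Working it through.** **The plan's own figures.** Protocol 11.1 takes 8 patients and a 25% DLT rate. P(at least 1) = 1 − 0.75^8 = 0.900. P(2 or more) = 1 − 0.75^8 − 8 × 0.25 × 0.75^7 = 0.633. Both match the stated 90% and 63%. They say nothing about when counts are drawn, and the point does not depend on them.

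**Inputs.**
- Panel 5 days: 1, 8, 15, 22, 29 (Appendix A). It includes platelets, white cells and differential (Appendix D), and SAP 8.4 makes it the source for laboratory-based hematologic toxicity.
- Draw time: within 15 minutes before dialysis (Appendix A, Footnote i, code [a]).
- Doses 1, 2 and 3: Days 1, 15 and 29, infused during dialysis. The Day 15 count therefore precedes dose 2, and the Day 29 count precedes dose 3.
- Week 4 visit: Day 22 ± 2.

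**Counts by cutoff.**

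| DLT cutoff | Post-baseline counts | After dose 2 | Consecutive pairs |
|---|---|---|---|
| Day 21 (current) | 8, 15 | 0 | 1 (8+15) |
| Day 22 | 8, 15, 22 | 1 | 2 (8+15, 15+22) |

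Under the current cutoff, an event under criterion 1, or the cytopenia part of criterion 2, that is confirmed by scheduled draws inside the window must be present on both Day 8 and Day 15.

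**Does the visit window rescue it?** Assume Mon/Wed/Fri or Tue/Thu/Sat dialysis. Dialysis days within Days 20 to 24 are:

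| Day 1 falls on | Possible Week 4 days | On or before Day 21 |
|---|---|---|
| Mon, Tue | 22, 24 | none |
| Wed, Thu | 20, 22, 24 | 20 |
| Fri, Sat | 20, 22 | 20 |

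A Day 20 count is possible for 2 of the 4 start days preferred in Protocol 5.3 (Thursday, Friday) and 2 of the 4 in Appendix A (Wednesday, Thursday). Even then it is a single count after dose 2.

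**What can the SRC see?** It reviews after all patients complete 21 days (Protocol 12, SAP 10.1). Take a patient dosed k days before the cohort's last patient. That patient's Day 22 comes 21 days after their own Day 1. The last patient's Day 21 comes k + 20 days after the same date. So Day 22 has been reached when 21 ≤ k + 20, that is, k ≥ 1. In a cohort opening a higher dose, the one active sentinel has k ≥ 2 because of the 48-hour hold, so this always holds for 1 of 8. For the other 7 it depends on enrollment stagger.

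**Exposure.** From Protocol Table 1 at 2 mg, adding first-dose Cmin to first-dose Cmax approximates the dose-2 peak: (712 + 268) / 712 = 1.38 times the dose-1 peak. The last-dose peak is 1640 / 712 = 2.30 times.

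**The case against.** Several points on the other side stand.

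- **The Grade 4/5 rule.** A reader might infer that a Grade 4 cytopenia first seen on Day 22 escapes both rules. The documents do not support that. Day 21 is attached to the MTD determination and to the SAP 8.3 table, while the single-event rule in Protocol 4.4 has no day limit. Section 4.4 also says that the escalation review will include 21 days of data, which can be read as a minimum. SAP 8.1 has the sponsor search laboratory listings for possible DLTs and states no cutoff. The text is unclear; it does not exclude a Day 22 event.
- **The neutrophil signal.** A reader might take Protocol 3.7 as evidence that neutropenia emerges at dose 2. It is not. Those changes came from a study in which three patients received a single 30 mg dose. They make neutrophils worth counting, and Days 8 and 15 are placed to see a single-dose effect.
- **Other oversight.** The SRC can halt for a trend and may see later counts from patients dosed earlier. Unscheduled visits are allowed. SAP 8.4 summarizes later hematology, and Protocol 9.3 summarizes neutropenia of Grade 2 or higher. This is a gap in the formal tally, not in monitoring as a whole.
- **A partial remedy.** One added count covers 2 of 6 doses, and the 15+22 pair still contains a pre-dose-2 value. Criterion 3 has a gap of its own: Appendix A schedules chemistry on Days 1 and 36 only in Weeks 1 to 6. Closing that would need a new sample.
- **Perhaps little left to change.** Doses through Cohort 5 are 2, 6 and 20 mg (Protocol Synopsis), SAP 1.2.3 lists no higher dose, and SAP 11 ties database lock to Cohort 6. The Protocol still permits 60 mg.

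These points lower the weight of the concern. They do not change the calendar or supply the missing confirmation rule.

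**Conclusion.** The point holds as a minor one with a cheap remedy. On nominal days the window has 2 post-baseline counts, 0 of them after dose 2, and 1 confirmable pair. The more-than-2-of-8 tally and the SAP 8.3 table for criterion 1, the cytopenia part of criterion 2 and laboratory-detected criterion 4 therefore normally describe dose 1. Whether a Day 22 event triggers the Grade 4/5 rule, and whether a count confirmed after Day 21 qualifies, is left open.

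This assumes thrice-weekly dialysis on the two usual patterns and no unscheduled counts. The documents do not allow an estimate of how many events would be missed, and none is claimed.

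Cohorts 1 to 5 contain two escalations to a new dose (2 to 6 mg and 6 to 20 mg). A third arises only if 60 mg is opened.

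**What to change.** Amend the Protocol Synopsis, 3.1, 3.2, 4.4 and 12, and SAP 1.2.2, 1.3.1, 8.3 and 10.1, as follows:

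1. Extend the DLT window for criteria 1, 2 and 4 to include the scheduled Week 4 (Day 22) pre-dialysis Panel 5 count. Name the criteria by number, because criteria 1 and 2 are labelled non-hematologic. Leave criteria 3 and 5 at Day 21.
2. State that a low count first seen in that window and confirmed at the next draw (a repeat at the next dialysis session, or Day 29) qualifies under criteria 1 and 2.
3. State that the same window applies to the Grade 4/5 no-escalation rule. Later events stay with the SRC's discretion to halt.
4. Apply this to any remaining escalation. For completed cohorts, keep the Day 21 tally as the pre-specified result and show the Week 4 tally beside it, labelled post hoc because the SRC reviews are unblinded.

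The cost is wording, with no new scheduled samples, and some delay to SRC review counted from Day 21:

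| Situation for the last patient | Delay |
|---|---|
| Week 4 visit on Day 22 | 1 day |
| Week 4 visit at the late edge, Day 24 | 3 days |
| Low Day 22 count repeated at next session (Day 24 or 25) | 3–4 days |
| Low Day 24 count repeated at next session (Day 26 or 27) | 5–6 days |
| Confirmation left to Day 29 | 8 days |

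If no dose above 20 mg is opened, the supplementary table from existing data is the only gain.
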